6.5.2.3 Progression-Free Survival (PFS)

PFS is defined as the time from the start of study treatment to the first documentation of PD or death due to any cause, whichever comes first.

The same censoring rules as outlined in Section 6.5.2.2 for DOR will be applied to PFS. Patients lacking an evaluation of tumor response after their first dose of study drug will have their event time censored at Day 1.

PFS will be analyzed by cohort using the Kaplan-Meier methodology and Kaplan-Meier plots will be provided. The median PFS and its 2-sided 90% CI will be calculated as appropriate. The PFS rates at 3 and 6 months, and every 3 months thereafter, will be reported and their 2-sided 90% CIs will be calculated.

Sensitivity analysis of PFS will be performed as described in Section 6.5.2.2 for DOR.

6.5.2.4 Overall Survival (OS)

OS is defined as the time from the start of study treatment to date of death due to any cause. In the absence of death, survival time will be censored at the last date the patient is known to be alive (i.e., date of last contact). Patients lacking data after their first dose of study drug will have their survival time censored at Day 1.

OS will be analyzed by cohort using Kaplan-Meier methodology and Kaplan-Meier plots will be provided. The median OS and its 2-sided 90% CI will be calculated as appropriate. The OS rates at 6 and 12 months, and every 6 months thereafter, will be reported and their 2-sided 90% CIs will be calculated.

6.6 Safety Analyses

All safety analyses will be performed by cohort and total using the safety analysis set.

Adverse events will be coded using Medical Dictionary for Regulatory Activities (MedDRA, Version 22.0 or higher).

Laboratory values will be graded according to the National Cancer Institute (NCI) Common Terminology Criteria for Adverse Events (CTCAE version 5.0 or higher).

Concomitant medications will be coded using WHO Drug Global (version: Mar 2019 B3 format or more recent).

6.6.1 Adverse Events

AEs will be summarized by MedDRA preferred term in descending frequency of occurrence unless otherwise specified. For incidence reporting, if a patient reports more than one AE that was coded to the same system organ class or preferred term, the patient will be counted only once for that specific system organ class or preferred term.

A treatment-emergent AE (TEAE) is defined as a newly occurring or worsening AE after the first dose of study treatment.

Summaries of AEs will be provided by cohort and total for the following:

- TEAEs
- Grade 3 or higher TEAEs
- TEAEs by system organ class and preferred term
- TEAEs by system organ class, preferred term and maximum severity. At each system organ class or preferred term, multiple occurrences of events within a patient are counted only once at the highest severity
- AEs related to study drug
- AEs leading to dose delay
- AEs leading to dose reduction
- AEs leading to unplanned dose adjustment
- AEs leading to treatment discontinuation
- AEs leading to death
- Infusion related reactions
- SAEs
- SAEs by system organ class and preferred term
- SAEs related to study drug
- Treatment-emergent Adverse Events of Special Interest (AESI) by system organ class, preferred term and maximum severity
- Treatment-emergent AESI
- Serious AESI

All AEs, SAEs, AEs leading to treatment discontinuation, and AEs leading to death will be listed.

6.6.1.1 Adverse Events of Special Interest (AESI)

Adverse events of peripheral neuropathy are considered AEs of special interest. Other AEs may also be added as AESI, as necessary.

Time to AE onset and time to resolution may be analyzed for treatment-emergent AESI, as appropriate. Patient level time to AE onset and time to resolution will be analyzed by cohort using Kaplan-Meier methodology. Treatment-emergent AESI outcomes will be tabulated. Only patients with treatment-emergent AESI events will be included in these analyses.

Time to onset of treatment-emergent AESI is defined as time from the date of first dose to start date of first treatment emergent AESI.

A treatment-emergent AESI is considered as resolved if the AESI has outcome of recovered/resolved or recovered/resolved with sequelae. For patients with multiple treatment-emergent AESI events, patient level resolution is defined as all treatment-emergent AESI events are resolved as defined above. Patient level time to resolution is defined as time from onset of first treatment-emergent AESI to the time of resolution of all treatment-emergent AESI events (i.e., end date of last resolved AESI event). Patients who do not have resolution for treatment-emergent AESI events will be censored at the date of last follow up.

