5.10 Timing of Analyses

The primary analysis will be conducted when all treated subjects in a cohort have been followed for at least 6 months or come off study, whichever comes first. Subsequent data cutoff dates may be defined to allow for more precise estimates of time-to-event endpoints.

Interim analysis for futility will be performed separately for each cohort after at least 12 subjects of a given cohort have been treated and are efficacy evaluable post-baseline.

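### The optional Kaplan-Meier analysis of time to neuropathy onset includes only patients who had the event, so its curve must end at 100% and its median is onset among affected patients, not risk over time

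*SAP*

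**What the plan says.** SAP 6.6.1.1 names the event: "Adverse events of peripheral neuropathy are considered AEs of special interest". Others may be added.

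The timing analyses are optional: "Time to AE onset and time to resolution may be analyzed for treatment-emergent AESI, as appropriate". If they are run, the method is fixed: "Patient level time to AE onset and time to resolution will be analyzed by cohort using Kaplan-Meier methodology". The population is then restricted: "Only patients with treatment-emergent AESI events will be included in these analyses".

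Onset is defined as follows: "Time to onset of treatment-emergent AESI is defined as time from the date of first dose to start date of first treatment emergent AESI". No censoring time is given for a treated patient who never develops neuropathy. The section's one censoring rule concerns resolution: "Patients who do not have resolution for treatment-emergent AESI events will be censored at the date of last follow up".

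The general rule in SAP 6.6 is different: "All safety analyses will be performed by cohort and total using the safety analysis set". That set is all treated patients (SAP 4.2). Section 6.6.1.1 departs from it without giving a reason.

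**The concern.** A Kaplan-Meier estimate of time to onset describes risk in everyone who could have had the event, with event-free patients contributing time until they are censored. Selecting patients because they had the event conditions on the outcome. What is left is the distribution of onset times among affected patients, and the Kaplan-Meier label invites reading it as risk over time.

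Two things are at stake. First, the curve and median cannot be read as the risk of neuropathy by a given month. Second, they cannot be compared between tumor cohorts whose follow-up differs, because follow-up alone moves the median. Such differences are likely: SAP 5.10 sets only a minimum ("The primary analysis will be conducted when all treated subjects in a cohort have been followed for at least 6 months") and also counts patients who have come off study earlier. This is the only analysis of neuropathy timing that the SAP describes.

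**Working it through.** The SAP gives no figure for this analysis, so there is none to reproduce. The check is algebra, then an illustration.

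**1. What the estimator becomes.** If all n patients included have an onset time, nothing is censored. Kaplan-Meier reduces to one minus the empirical distribution, so cumulative onset is exactly 100% at the last onset. With common follow-up τ and true cumulative incidence F(t), the planned curve estimates F(t)/F(τ). That is never below F(t), and it equals 1 at τ whatever F(τ) is.

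**2. Inputs for scale (assumptions).** The documents give no neuropathy incidence for this trial. Protocol Tables 1 and 2 give peripheral sensory neuropathy, a single preferred term, in a different trial in metastatic breast cancer:
- q3wk, pooled over doses: 69/191 = 36.1%
- q1wk: 3/20 = 15.0% at 1.0 mg/kg, 28/52 = 53.8% at 1.25 mg/kg, 5/9 = 55.6% at 1.5 mg/kg

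I take 15% to 56% as an assumed range for the proportion p affected by τ = 6 months, with a constant hazard.

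**3. Formulas.** Hazard λ = −ln(1 − p)/τ. All-treated median = ln 2/λ. Events-only median = −ln(1 − p/2)/λ. Cumulative onset at 3 months = 1 − exp(−3λ) for all treated, and that value divided by p for events only.

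For p = 0.361: λ = 0.4478/6 = 0.0746 per month. All-treated median = 0.6931/0.0746 = 9.3 months, beyond follow-up. Events-only median = −ln(0.8195)/0.0746 = 2.7 months. At 3 months: 20.1% against 20.1/36.1 = 55.6%.

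| p by 6 months | All-treated curve ends at | All-treated median (months) | Events-only curve ends at | Events-only median (months) | 3-month onset: all treated / events only |
|---|---|---|---|---|---|
| 15.0% | 15.0% | 25.6 (not reached) | 100% | 2.9 | 8% / 52% |
| 36.1% | 36.1% | 9.3 (not reached) | 100% | 2.7 | 20% / 56% |
| 53.8% | 53.8% | 5.4 | 100% | 2.4 | 32% / 60% |
| 55.6% | 55.6% | 5.1 | 100% | 2.4 | 33% / 60% |

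Incidence varies nearly fourfold, yet the events-only median moves only from 2.9 to 2.4 months.

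**4. Effect of follow-up alone.** Keep λ = 0.0746 and extend follow-up to 12 months: F(12) = 1 − 0.639² = 59.2%. The events-only median is −ln(1 − 0.592/2)/0.0746 = 4.7 months, against 2.7 months with 6 months of follow-up. The hazard is identical; a cohort followed for longer simply appears to have later onset.

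**5. Staggered follow-up.** In 4,000 simulated cohorts of 30, with assumed uniform censoring between 1 and 8 months and 6-month incidences of 15%, 36.1% and 44.4% (the last being 36/81, q1wk pooled), every events-only curve with at least one event ended at exactly 100%. The events-only median was about 1.9 months in all three settings. The all-treated curves ended on average at about 19%, 43% and 52%.

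Those endpoints are not the crude proportions. For the 36.1% setting the expected crude proportion is 1 − [exp(−λ) − exp(−8λ)]/(7λ) = 1 − (0.928 − 0.550)/0.522 = 28%, and the true 8-month risk is 1 − exp(−8λ) = 45%. The all-treated curve tracks the true risk and lies above the crude share.

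**The case against.** The strongest reply is that little depends on this analysis. It is optional and descriptive, and no objective, stopping rule or primary endpoint uses it. SAP 6.6.1 separately tabulates treatment-emergent and serious AESI, and SAP 6.6 puts those tables on the safety analysis set, so the report will still show the true proportion affected. The restriction is stated openly. With no censoring, the Kaplan-Meier median is essentially the ordinary median among affected patients, which is a legitimate summary if labelled as such. All of this stands and limits the weight of the point. It does not rescue the curve: if the analysis is run, its method is fixed, and the incidence tables show how many patients were affected, not when.

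It could also be argued that the restriction was meant for resolution and outcomes only. The plural wording follows a sentence that names onset, and no censoring rule for onset exists, so the natural reading includes onset.

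A reader might go further in four ways that the documents do not support:
- **That the trial will report neuropathy as universal.** The incidence tables prevent this.
- **That a comparison of dosing schedules will be distorted.** The SAP is written to the protocol version of 22 April 2019, with one q3wk regimen and a single arm (SAP 1, 3 and 5.3), and plans no such comparison. This would matter only if the method were carried into the later parts of the protocol.
- **That dose holds or reductions depend on it.** Those follow each patient's own grade (Protocol 5.2.4).
- **That the corrected curve would end at 36% to 44%, with more than half of patients left out.** These are crude, dose-pooled figures for one preferred term in another trial. At 1.25 and 1.5 mg/kg q1wk in Protocol Table 2, 53.8% and 55.6% were affected, so fewer than half would be excluded; at 1.0 mg/kg, 85% would be.

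**Conclusion.** The point holds for time to onset only. As written, the onset curve has no censoring, ends at 100% by construction, and gives a median conditional on having the event. That median is earlier than in the treated population and depends on follow-up. It cannot be read as risk over time or compared across cohorts followed for different lengths of time.

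The 100% endpoint needs no assumption. The sizes do: under a constant hazard, 6 months of common follow-up and an assumed 15% to 56% affected, 3-month onset would read 52% to 60% instead of 8% to 33%. Real values depend on the hazard, the follow-up and the incidence in these tumor types.

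The consequence is confined to an optional descriptive safety display. The AESI incidence tables, the primary endpoint and the futility rule are untouched. Restricting time to resolution to affected patients is correct.

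**What to change.** Amend SAP 6.6.1.1 as follows:
- **Onset:** use the safety analysis set. Censor patients without a treatment-emergent AESI at the end of the AE reporting period (Protocol 7.6.1.3) or last follow-up, whichever is earlier. Alternatively, estimate cumulative incidence with death as a competing event.
- **Resolution and outcome tabulations:** keep the restriction to patients with an event, and say that it applies to these only.
- **Onset among affected patients, if wanted:** report the median and range, labelled as conditional on having the event, and not as Kaplan-Meier.

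The cost is a few lines of SAP wording and the matching table and figure specification. No additional data are needed, because first-dose, AE-start and follow-up dates are already collected.

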5.2.4.2. Part B (q1wk dosing) and Part C (Arm 3; q1wk dosing)

In the event of an AE or lab criteria that prevents dosing of LV (see Section 5.2.3.1), the LV dose for the week should be withheld. LV may be resumed when the dosing criteria are met. If a dose(s) of LV is withheld, the corresponding visit may be skipped and resume the following week (eg, if the Day 8 dose is skipped, visits will resume on Day 15; if Day 8 and Day 15 doses are skipped, visits will resume on Day 1 of the following cycle). Day 1 of a cycle may be delayed but not skipped.

Dose reduction of LV may be considered in the event of recurrent AE despite withheld doses. Dose re-escalation following dose reduction is not allowed. Dose levels for LV dose reductions in Part B and Part C (Arm 3) are shown in [Table 11](#).

For Part C (Arm 3), subjects who discontinue pembrolizumab due to a pembrolizumab-related AE (see Section 5.3.4) may continue LV. Similarly, subjects who discontinue LV for a LV-related AE may continue pembrolizumab. See Section 5.5.3 for details on managing overlapping AEs.

Table 11: Q1wk LV dose reductions

Starting Dose	First Dose Reduction (mg/kg/wk)	Second Dose Reduction (mg/kg/wk)
Starting dose 1.0 mg/kg/wk	0.75	0.5
Starting dose 1.25 mg/kg/wk	1.0	0.75

For nonclinical events requiring alteration in dosing schedule (eg, holidays, scheduling conflicts), a +2 day dosing window is allowed. Nonclinical events that require skipping a dose(s), must be approved by sponsor medical monitor. At least 7 days must elapse between each administration of LV.

Dose modification guidelines for LV q1wk treatment-associated toxicity are detailed in [Table 12](#).

Table 12: Dose modifications for LV treatment-associated toxicity (Part B and Part C [Arm 3] q1wk dosing)

Toxicity	Grade 1	Grade 2	Grade 3	Grade 4
Peripheral neuropathy ^a	Continue at same dose level	Withhold until toxicity resolves to \leq Grade 1; treatment may resume at the next lower dose level (see Table 11)	Withhold until toxicity resolves to \leq Grade 1, then resume treatment at the next lower dose level (see Table 11)	Discontinue treatment
Hyperglycemia		Hold for blood glucose >250 mg/dL or >13.9 mmol/L. Resume treatment once elevated blood glucose has improved to ≤ 250 mg/dL or ≤ 13.9 mmol/L and subject is clinically and metabolically stable (see Section 5.6 for details).		

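### The SAP's time to resolution of neuropathy measures time until every event has resolved: for patients with separate episodes, the gaps count as unresolved and a later event overrides an earlier recovery.

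*SAP*

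**What the plan says.** SAP 6.6.1.1 names one event type: "Adverse events of peripheral neuropathy are considered AEs of special interest". For a patient with several events, "patient level resolution is defined as all treatment-emergent AESI events are resolved as defined above". The time reported is "time from onset of first treatment-emergent AESI to the time of resolution of all treatment-emergent AESI events", which the SAP equates with the "end date of last resolved AESI event". For everyone else, "Patients who do not have resolution for treatment-emergent AESI events will be censored at the date of last follow up".

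The analysis is optional: "Time to AE onset and time to resolution may be analyzed for treatment-emergent AESI, as appropriate". If done, it is a Kaplan-Meier summary by cohort, restricted to patients with a treatment-emergent event. The only other resolution output is a tabulation without durations: "Treatment-emergent AESI outcomes will be tabulated". Neither SAP 6.6.1 nor Protocol 9.3.8 gives a rule for gaps between episodes, a per-episode duration or another definition.

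Protocol 5.2.4 (Tables 10, 12 and 14) withholds LV for Grade 2 or 3 neuropathy until it is Grade 1 or lower, after which dosing resumes at a lower level. The Grade 2 entry of Table 12 reads "treatment may resume at the next lower dose level".

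**The concern.** There is a single clock with no stop between episodes. This has two consequences.

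- **Interpretation.** A reader will take time to resolution as how long neuropathy lasts. For a patient with two separate episodes it also includes the neuropathy-free interval between them.
- **Method.** Kaplan-Meier needs a patient's status at time t to be settled by what has happened up to t. Here a patient who recovers on day 40 is an event at day 40 if follow-up ends before any relapse. If a new episode starts on day 300, the same patient counts as unresolved throughout. The estimated chance of resolution by a fixed time can therefore depend on how long patients are observed.

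Peripheral neuropathy is the only named event of special interest, and Protocol 7.6.1.3 singles it out for possible extended follow-up. Its reversibility is a result that readers will look for. The primary endpoint, sample size and futility rule are not touched.

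**Working it through.** The plan states no figure here, so there is none to reproduce. The rule was applied literally to an example and then simulated.

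**Example (assumed dates).** Episode 1 runs on days 60-90 and episode 2 on days 200-221. SAP 5.4.1 sets duration as end minus start plus 1.

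- Days with neuropathy: (90 - 60 + 1) + (221 - 200 + 1) = 31 + 22 = 53.
- SAP rule: 221 - 60 + 1 = 162.
- Days between episodes: 200 - 90 - 1 = 109, and 53 + 109 = 162.

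If episode 2 never resolved, the patient would be censored as unresolved, although episode 1 cleared in 31 days.

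**Who enters the analysis.** Protocol 1.2.4.3 reports peripheral sensory neuropathy in 36.1% on q3wk (Table 1) and 53.8% at 1.25 mg/kg q1wk (Table 2). If those rates carried over:

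- Part A, capped at 12 per cohort: 0.361 x 12 = 4.3 subjects.
- A cohort of 30 on q3wk: 0.361 x 30 = 10.8.
- A cohort of 30 at 1.25 mg/kg q1wk: 0.538 x 30 = 16.1.

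Only those with separate episodes are affected. At an assumed 20-50% recurrence, that is about 1-2 subjects in a Part A cohort (4.3 x 0.2 = 0.9; 4.3 x 0.5 = 2.2).

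**Simulation.** All of the following are assumptions, because the documents give none of these quantities:

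- exponential episodes with a median of 60 days;
- at most one recurrence, with probability 20-50%;
- exponential gap with a median of 60-120 days;
- follow-up uniform over 180-540 days after first onset.

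The first-episode median is 60 days, and resolution by day 180 is 1 - 2^(-180/60) = 87.5%. The drift column uses 30% recurrence and a 120-day gap. It shows the change in 180-day resolution under the SAP rule when mean follow-up grows from 300 to 730 days.

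| New episodes captured until | SAP-rule median, days | Drift in 180-day resolution |
|---|---|---|
| End of follow-up | 77-128 | 75% to 69% |
| 90-365 days after first onset | 72-110 | about 1 point |
| 30-180 days after first onset | 66-83 | none |

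With capture to the end of follow-up, 180-day resolution under the SAP rule is 64-78%.

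A second set of assumptions (30-day median episode, 20-40% recurrence, follow-up 120-360 days) gives SAP-rule medians of 38-55 days against 30. With no recurrence the two rules agree.

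**The case against.** The strongest reply is that this is a choice of estimand. The SAP states openly that it measures time until all events have resolved, which is consistent and conservative for safety. A first-episode measure used alone would count a patient with a permanent relapse as resolved. This stands, and it is why the existing measure should be kept.

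Two further objections also stand in large part.

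- **Recurrence.** A reader might infer from the hold-and-restart rule that separate episodes are to be expected. The documents do not support that. Dosing may resume once neuropathy is Grade 1, and Grade 1 neuropathy is not an event with a resolved outcome. That course is one continuous neuropathy with changing grade. SAP Appendix A shows one adverse event held as several graded log lines, and for such records the SAP rule gives the true span. Separate episodes are possible, but nothing shows that they are common.
- **Data cuts.** A reader might infer that successive cuts will not be comparable. Protocol 7.6.1.3 collects new non-serious events only to the end-of-treatment visit or 30 days after last treatment, whichever is later (90 days in Part C Arms 2 and 3). The extended follow-up of neuropathy is for events already recorded. Material drift therefore needs long treatment, with new episodes captured throughout.

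The outcome tabulation, the adverse event listings and the optional status of the analysis soften the problem. None of them supplies a duration per episode.

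**Conclusion.** The point holds as a limited one. The SAP wording produces time until all neuropathy events have resolved and applies Kaplan-Meier to a status that later events can change. For patients with separate episodes it overstates how long neuropathy lasted: 162 days against 53 in the example.

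The size in this trial is unknown. Under the 60-day, 20-50% recurrence assumptions the SAP-rule median is about 66-128 days against 60. The upper end requires new episodes to be captured throughout follow-up. Drift between cuts ranges from none to about 6 points (75% to 69%) on the same condition. The effect vanishes without separate episodes.

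The analysis is descriptive and optional, so no decision rule is at risk. The reason to act is that the figure, as labelled, would be misread, and the correction is cheap.

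**What to change.** In SAP 6.6.1.1:

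1. Keep the present measure, labelled *time to resolution of all neuropathy events*.
2. Add a Kaplan-Meier time from first treatment-emergent onset to the first date with no treatment-emergent neuropathy ongoing, censored at last follow-up if there is no such date. Merge records into one episode if they overlap, or if the end date of one and the start date of the next are no more than 1 day apart.
3. Report the number and proportion of patients with a later episode, and total days with neuropathy, beside it, so that the first-episode figure cannot overstate reversibility.

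Onset dates, resolution dates and outcomes are already collected under Protocol 7.6.1.2. The cost is SAP wording, some programming and a few extra table rows.

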6. STUDY ACTIVITIES

6.1. Schedule of Events

A schedule of events is provided in [Appendix A](#) for baseline/screening and in [Appendix B](#), [Appendix C](#), and [Appendix D](#) for treatment. Study activities are listed by visit in this section and descriptions of all study assessments are presented in Section 7. AEs and concomitant medications will be recorded from Day 1 (predose) through the safety-reporting period (end of treatment [EOT] visit or 30 days after the last study treatment, whichever is later, with the exception of AEs of interest, which will be followed until resolution, death, or withdrawal of consent; see Section 7.6.1.3). Any study protocol-related AE (defined in Section 7.6.1.1) as well as any concomitant medications given for the treatment of the AE, should be recorded from the time of informed consent.

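### If time to resolution of neuropathy is analysed, the SAP's Kaplan-Meier rule censors patients who die unresolved, and with complete neuropathy follow-up the curve then overstates recovery

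*SAP*

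**What the plan says.** SAP 6.6.1.1 names one AESI: "Adverse events of peripheral neuropathy are considered AEs of special interest". Others may be added. The analysis is optional: "Time to AE onset and time to resolution may be analyzed for treatment-emergent AESI, as appropriate". The method, if the analysis is run, is fixed: "Patient level time to AE onset and time to resolution will be analyzed by cohort using Kaplan-Meier methodology". The analysis is limited to patients who had such an event ("Only patients with treatment-emergent AESI events will be included in these analyses"). Resolution means that all of a patient's events have resolved, with or without sequelae.

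A patient who has not resolved is handled by a single rule: "Patients who do not have resolution for treatment-emergent AESI events will be censored at the date of last follow up". There is no separate rule for death, and neither document names a competing-risk method. The section also plans a simple table: "Treatment-emergent AESI outcomes will be tabulated".

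The protocol describes the length of follow-up in two ways. Section 6.1 refers to "AEs of interest, which will be followed until resolution, death, or withdrawal of consent". Section 7.6.1.3 only permits extended follow-up of non-serious events of interest, neuropathy in particular. It gives the end points as resolution, return to baseline or study closure, and does not list death. Survival contact under Protocol 6.7 runs to death or study closure and may be by telephone.

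**The concern.** Under the SAP rule, a patient who dies with neuropathy is censored like one who is alive and still under observation. Kaplan-Meier then assumes that the dead patient would have gone on to resolve at the rate seen in survivors. One minus the curve describes resolution in a population without deaths. In advanced cancer, deaths before resolution are likely to be common, so the curve and its median would make neuropathy look more reversible than it was for the patients treated. This is the one toxicity that the SAP singles out, and Protocol Tables 10, 12 and 14 tie treatment modification to it.

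**Working it through.** The plan states no resolution probability, median or death rate, so there is no figure of its own to reproduce.

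**Inputs from the documents.** The SAP covers 2.5 mg/kg q3wk, with up to 30 subjects per cohort (SAP 3 and 5.2). Protocol Table 1 (q3wk) gives peripheral sensory neuropathy in 69/191 = 36.1%. Expected patients in the analysis: 30 × 0.361 = 10.8, about 11 per cohort. Protocol 9.1 now limits Part A cohorts to 12, which gives 12 × 0.361 = 4.3, about 4.

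**Assumptions.** Exponential times from neuropathy onset, with r = ln2/(median resolution) and d = ln2/(median survival).

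- Kaplan-Meier with deaths censored estimates 1 − exp(−rt).
- The probability of having resolved by t, with death competing, is r/(r+d) × [1 − exp(−(r+d)t)].

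**Worked case: medians 6 months (resolution) and 9 months (death).** r = 0.1155, d = 0.0770, r/(r+d) = 0.60.

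- 6 months: Kaplan-Meier 50.0%; cumulative incidence 0.60 × 0.685 = 41.1%; excess 8.9 points.
- 12 months: 75.0% against 0.60 × 0.901 = 54.0%; excess 21.0 points.
- Median: Kaplan-Meier gives 6 months. Cumulative incidence reaches 50% when exp(−(r+d)t) = 1/6, so t = ln6/0.1925 = 9.3 months.

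**Range.** Over resolution medians of 4 to 9 months and survival medians of 6 to 18 months, the excess is 3.7 to 15.3 points at 6 months and 10.3 to 29.4 points at 12 months.

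**Small samples.** In simulated cohorts of 11 under four pairs of medians, one minus Kaplan-Meier was never below the cumulative incidence. It was strictly above it at 12 months in 78% to 98% of cohorts.

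**Against noise.** In the worked case the simulated standard error of the 6-month Kaplan-Meier estimate is 16 points at n = 13. Scaled to n = 11 it is 16 × √(13/11) = 17 points, larger than any 6-month excess in the range. At 12 months about 11 × exp(−0.1925 × 12) = 1.1 patients remain at risk.

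**The undefined censoring date.** Simulated 12-month probability of resolution, with medians of 6 months (resolution) and 12 months (death):

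| Median length of neuropathy follow-up | True | Censored at last survival contact | Censored at last neuropathy assessment |
|---|---|---|---|
| 6 months | 58.2% | 46.6% | 74.7% |
| 12 months | 58.4% | 58.3% | 75.1% |
| 24 months | 58.3% | 65.9% | 74.9% |

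If patients stay at risk to last survival contact after neuropathy assessment has stopped, unseen resolutions pull the curve down. This can offset the effect of censoring deaths or outweigh it.

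**The case against.** The strongest reply is that this is an optional, descriptive safety display, and that the output reporting recovery most directly is sound. The AESI outcome table gives a crude proportion that censoring does not touch. Deaths are summarised and listed under SAP 6.6.3. The SAP asks for landmark rates for PFS and OS but for none on neuropathy resolution. In one cohort the 6-month bias is smaller than the noise. All of this stands. It limits the weight of the point but does not make the censoring rule right: the method is prescribed once the analysis is chosen, and a curve and median are what such an analysis yields. The table has no time axis and would disagree with the curve without explanation. Nor does a larger sample shrink a bias. SAP 6.6 calls for safety analyses by cohort and in total, and any pooled curve would carry the same bias with less noise around it.

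A reader might infer that every reported chance of recovery will be too high. The outcome table rules that out. A reader might also infer that the direction is certain. It is not, because the SAP does not define the date of last follow-up and Protocol 6.1 and 7.6.1.3 differ. Nor do the documents rank neuropathy as LV's main lasting toxicity; they make it the only named AESI and single it out for longer follow-up. The dose-modification rules depend on grade, not on this curve.

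**Conclusion.** The point holds conditionally. If the analysis is performed and neuropathy is followed completely, censoring deaths makes the curve too high and the median too short. The size is not in the documents: about 4 to 15 points at 6 months and 10 to 29 points at 12 months, under constant hazards and the assumed medians. In a single q3wk cohort the 6-month gap cannot be told from sampling error, and at 12 months almost no one remains at risk. If patients are kept at risk to last survival contact, the bias may shrink or reverse. The primary endpoint, the futility rule and the sample size are untouched. The change is worth making because the stated rule is wrong for the quantity a reader will want, and the remedy is cheap.

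**What to change.** In SAP 6.6.1.1:

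- Estimate patient-level resolution by cumulative incidence (Aalen-Johansen), with death before resolution as a competing event.
- Replace the undefined date: censor patients who are alive and unresolved at their last neuropathy assessment. State how a death after assessment has stopped is handled.
- Next to the planned outcome table, give the numbers resolved, alive and unresolved, and dead and unresolved.

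Reconcile Protocol 6.1 with 7.6.1.3 on how long neuropathy is followed.

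The cost is wording and a standard procedure on data already collected. The last-assessment date may need a derivation rule, since Protocol 7.6.1.2 lists onset date, resolution date and outcome for each event but no status date. The downside is that the reported resolution figures become somewhat less favourable.
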